## NCI CTCAE grading

NCI CTCAE grades will be derived programmatically for applicable laboratory parameters. The programmatically derived grades will be used for summary tables.

As applicable, values will be converted to standard units and will be graded using NCI CTCAE V5.0.

## **Lymphocytosis**

Lymphocytosis is defined as an ALC > 5000 cells/ $\mu$ L and an increase 50% or more from baseline.

Duration of lymphocytosis is defined as the duration of time from the earliest date on which the ALC value met the lymphocytosis criteria at a post-baseline assessment to the earliest date on which a subsequent ALC value met the resolution criteria.

For patients with lymphocytosis, resolution of lymphocytosis is defined as 1) a decrease of ALC value to the baseline level or lower, or 2) an achievement of ALC value that is below 5,000/ $\mu$ L, whichever occurs first.

## **4. ANALYSIS METHODS**

### **4.1 General Principles**

The primary objective of the study is to test the following hypothesis:

H0: BICR-assessed PFS of Arm A is the same as Arm B

H1: BICR-assessed PFS of Arm A is not the same as Arm B

The study will be considered positive (a success) if the primary PFS analysis result for Arm A versus Arm B is statistically significant.

The below mentioned general principles will be followed throughout the study:

- Descriptive statistics will be used for all variables, as appropriate. Continuous variables will be summarized by the number of observations, mean, standard deviation, median, upper and lower quartiles minimum, and maximum. For log-transformed data it is more appropriate to present geometric mean, coefficient of variation (CV), median, minimum and maximum. Categorical variables will be summarized by frequency counts (n) and percentages (%) for each category.
- Unless otherwise stated, percentages will be calculated out of the total number of patients in the analysis set for the corresponding treatment group. Overall totals (i.e. data from Arm A and Arm B combined) will be calculated for baseline summaries only.
- For continuous data, the mean and median will be rounded to 1 additional decimal place compared to the original data. The standard deviation will be rounded to 2 additional

decimal places compared to the original data. Minimum and maximum will be displayed with the same accuracy as the original data.

- For categorical data, percentages will be rounded to 1 decimal place.
- SAS® version 9.4 will be used for all analyses.

In general, for efficacy and CCI (except for laboratory parameters) the last observed measurement prior to randomization will be considered the baseline measurement. However, if an evaluable assessment is only available after randomization but before the first dose of randomized treatment then this assessment will be used as baseline. For laboratory parameters used for efficacy parameters, the last observation before the first dose of study drug will be used. However, if the randomized patient never received any study treatment, the last assessment prior to randomization will be used. For safety endpoints the last observation before the first dose of study drug will be considered the baseline measurement unless otherwise specified. For demography and disease characteristics of subjects who did not receive treatment, the last observed measurement prior to randomization will be used as the baseline measurement. For analyses of subjects who crossover to acalabrutinib baseline for safety endpoints will be defined as the last assessment prior to the first dose of crossover therapy.

For assessments on the day of first dose where time is not captured, a nominal pre-dose indicator, if available, will serve as sufficient evidence that the assessment occurred prior to first dose. Assessments on the day of the first dose where neither time nor a nominal pre-dose indicator are captured will be considered prior to the first dose if such procedures are required by the CSP to be conducted before the first dose.

If two visits are equally eligible to assess patient status at baseline (e.g., screening and baseline assessments both on the same date prior to first dose with no washout or other intervention in the screening period), the average can be taken as a baseline value. For non-numeric assessments where taking an average is not possible then the best value would be taken as baseline as this is the most conservative. In the scenario where there are two assessments on day 1, one with time recorded and the other without time recorded, the one with time recorded would be selected as baseline. Where safety data are summarized over time, study day will be calculated in relation to date of first treatment.

In all summaries change from baseline variables will be calculated as the post-treatment value minus the value at baseline. The percentage change from baseline will be calculated as  $(\text{post-baseline value} - \text{baseline value}) / \text{baseline value} \times 100$ .

Endpoints will be summarized and analyzed using the analysis sets indicated in Table 2.

## 4.2 Analysis Methods

The following table (Table 7) details which endpoints are to be subjected to formal statistical analysis, together with pre-planned sensitivity analyses, making it clear which analysis is regarded as primary for that endpoint.

**Table 7 Formal Statistical Analyses to be Conducted and Pre-planned Sensitivity Analyses**

Endpoints Analyzed	Notes
PFS	
Primary analysis: Stratified log-rank test adjusted for ECOG (0-1 versus 2) and Rai stage (Stage 0-II versus III-IV) with BICR defined response
 
Sensitivity analyses a
 
 
1. Unstratified log-rank test
 
2. Analysis of alternative censoring rule - without censoring prior to subsequent therapies
 
3. Analysis of alternative censoring rule – without censoring prior to two or more consecutively missed response evaluations
 
4. Ascertainment bias analysis - using investigator assessments
 

Overall response rate	CMH chi-square test adjusted for ECOG (0-1 versus 2) and Rai stage (Stage 0-II versus III-IV) using both BICR and investigator defined responses
Duration of response	Stratified log-rank test adjusted for ECOG (0-1 versus 2) and Rai stage (Stage 0-II versus III-IV) using both BICR and investigator defined responses
Time to next therapy	Stratified log-rank test adjusted for ECOG (0-1 versus 2) and Rai stage (Stage 0-II versus III-IV)
Overall survival	
Stratified log-rank test adjusted for ECOG (0-1 versus 2) and Rai stage (Stage 0-II versus III-IV)
 
Sensitivity analysis considering censoring crossover patients prior to receiving acalabrutinib monotherapy

Minimal residual disease	CMH chi-square test adjusted for ECOG (0-1 versus 2) and Rai stage (Stage 0-II versus III-IV)

a See 4.2.2.2 for further details

#### **4.2.1 Multiplicity**

To control the overall type I error at 0.05 level, the Lan-Demets alpha spending function based on the O’Brien-Fleming boundary is used to split alpha for the interim and final analyses of PFS. If exactly 76% of PFS events at final is available at the time of the interim analysis, that is 38/50 PFS events based on BICR have occurred, the 2-sided alpha level to be applied for the interim and the final analysis will be 0.02 and 0.044, respectively. The nominal alpha levels for the interim and final analyses will be determined based on actual number of PFS events observed at the time of the analyses.

## **4.2.2 Efficacy analyses**

All efficacy analyses will use the FAS unless otherwise specified.

### **4.2.2.1 Time-to-event endpoint considerations**

#### **Pooling Strategy**

Stratified log-rank tests and Cox proportional hazards model will adjust for the following factors:

- ECOG (0-1 versus 2)
- Rai stage (Stage 0-II versus III-IV)

There are at least 2 events per treatment group in each stratum (where a stratum is defined as stratification factor 1 \* stratification factor 2), stratification factors should be collapsed until all strata have at minimum two events for the primary endpoint. Stratification factors will be removed from the model in the following order, until at least 2 events per treatment group in each stratum are available:

- Rai stage (Stage 0-II versus III-IV)
- ECOG (0-1 versus 2)

All analyses will then be conducted in accordance with the pooling strategy defined for the primary analysis.

If there are secondary endpoints that still will not conform to the requirement on number of events above defined, unstratified log-rank tests and Cox proportional hazards model will be used for the analysis of the secondary endpoint. This will be supported by unstratified sensitivity analyses of the primary endpoint.

#### **Kaplan Meier analysis**

The median time-to-event will be presented for each treatment arm alongside its 95% confidence interval calculated using the Brookmeyer and Crowley technique and the stratified log-rank test for comparing the treatment arms.

Kaplan-Meier plots of time-to-event endpoints will be presented which will display the survival curves, the number of patients at risk, the median time-to-event and the 95% confidence intervals for each treatment arm.

#### **Hazard ratio and confidence interval estimation**

Time-to-event endpoints will be analyzed using a 2-sided stratified log-rank test adjusting for ECOG (0-1 versus 2) and Rai stage (Stage 0-II versus III-IV) for generation of the p-value.

The stratification variables in the statistical modelling will be based on the values entered into IRT/RTSM at randomization, even if it is subsequently discovered that these values were incorrect.

HR will be calculated from a stratified Cox proportional hazards model together with its corresponding, 95% CI. Treatment is the only covariate, ties are handled by the Efron approach and the CI is calculated using a profile likelihood approach.

### **Supporting summary measures**

Survival rates, estimated from the KM curve, will also be presented at 6 monthly intervals, starting at 6 months and finishing at the last 6-monthly interval prior to the maximum event time.

#### **4.2.2.2 Progression free survival (PFS)**

The primary analysis will compare PFS according to the hypotheses in [Section 4.1](#) and as assessed by BICR per IWCLL 2018 criteria using the methods described in [Section 4.2.2.1](#).

#### **Proportionality assumption**

The assumption of proportionality of hazards will be assessed. Proportional hazards will be tested firstly by examining plots of complementary log-log (event times) versus log (time) and, if these raise concerns, by fitting a time dependent covariate (adding a treatment-by-time interaction term) to assess the extent to which this represents random variation. If a lack of proportionality is evident, the variation in treatment effect can be described by presenting piecewise HR calculated over 6-monthly time-periods. In such circumstances, the HR from the primary analysis can still be meaningfully interpreted as an average HR over time unless there is extensive crossing of the survival curves. If lack of proportionality is found this may be a result of a treatment-by-covariate interaction, which will be investigated.

#### **PFS sensitivity analyses**

The following sensitivity analyses will be performed:

- In addition to the stratified primary analysis the unstratified log rank test and unstratified hazard ratios will be calculated.
- The primary analysis will also be repeated without PFS censoring to subsequent therapies. Therefore, patients who receive a subsequent therapy prior to progression or death will be assigned an event time according to their recorded progression or death date. Patients who receive a subsequent therapy and did not progress or die will be censored according to the rules in table 4 other than the subsequent therapy rule.

- The primary analysis will be repeated except that the actual PFS event times, rather than the censored times, of patients who progressed or died in the absence of progression immediately following two, or more, tumor assessments will be included. This will be supported by a Kaplan-Meier plot of the time to censoring where the censoring indicator of the primary PFS analysis is reversed (what was originally a censored event in the primary PFS analysis becomes an actual event and what was originally a PFS event becomes a censored event) will be presented.
- Ascertainment bias will be assessed by analyzing the investigator data. The stratified log rank test will be repeated on PFS using the investigator data based upon IWCLL 2018. The HR and CI will be presented.
- Concordance between Investigator and BICR assessed progression will be presented for each treatment group.

If there is an important discrepancy between the primary analysis using the BICR data and this sensitivity analysis using investigator data then the proportion of patients with site confirmation but no central confirmation of progression will be summarized; such patients have the potential to induce bias in the central review due to informative censoring. An approach of imputing an event at the next visit in the central review analysis may help inform the most likely HR value ([Fleischer et al 2011](#)), but only if an important discrepancy exists.

The primary analysis may also be repeated using the randomization strata as entered into the database rather than those entered into the IVRS system, but only if the proportion of patients with a discrepancy is more than 10%.

### **Additional supportive summaries**

In addition, the number of patients prematurely censored will be summarized by treatment arm together with baseline prognostic factors of the prematurely censored patients. A patient would be defined as prematurely censored if they had not progressed (or died in the absence of progression) and the latest scan prior to DCO was more than one scheduled tumor assessment interval plus 2 weeks prior to the DCO date.

Additionally, summary statistics will be given for the number of days from censoring to DCO for all censored patients.

A summary of the duration of follow-up will be provided using median time from randomization to date of censoring (date last known to have not progressed) in censored (not progressed) patients only, presented by treatment group.

Summaries of the number and percentage of patients who miss two or more consecutive tumor assessments will be presented for each treatment group.

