**Figure 1 Study design**

### 1.3 Number of Patients

Under the exponential model assumptions, the study is expected to randomize approximately 75 patients per arm (150 patients in total from both arms) with 1:1 randomization ratio. It is planned to randomize approximately 75 to 120 patients in total (50% to 80% of total sample size) from China. Randomization will be stratified by ECOG [0-1 versus 2] and Rai stage [0-II versus III-IV]. The study is sized to achieve more than 95% power to detect a hazard ratio of 0.333 in PFS (which translates into an improvement in median PFS from 30 months to 90 months) at the 2-sided significance level of 0.05, allowing for one interim analysis conducted at approximately 76% of the target events. The sample size calculation assumes a median PFS of 30 months in Arm B ([Michallet et al 2018](#)).

The final analysis of BICR-assessed PFS is event-driven and will be conducted when enrollment is completed and there are approximately 50 BICR-assessed PFS events in total from Arm A and Arm B. The accrual period is assumed to be approximately 30 months. The dropout rate is assumed to be 5% by 14 months for both arms. The interim and final analysis are anticipated to occur approximately 40 months and 53 months, respectively, after the first patient is randomized.

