#### 4.2.2.7 Overall survival (OS)

OS will be analyzed using the methods described in [Section 4.2.2.1](#).

The status of patients at the time of analysis will be summarized. This will include the number (%) of patients who died, the number (%) still in survival follow-up and the number (%) of patients who discontinued the study prior to death. Patients who discontinued the study prior to death will be further broken down by presenting the number (%) of patients who discontinued voluntarily, the number (%) of patients lost to follow-up and the number (%) of patients who discontinued the study for any other reason.

A sensitivity analysis for OS will also be performed where patients who received crossover therapy will be censored one day prior to the first dose of crossover therapy.

The number of patients prematurely censored will be summarized by treatment arm. A patient would be defined as prematurely censored if their survival status was not defined at the DCO.

In addition, duration of follow-up will be summarized using medians:

- In all patients: time from randomization to the date of death (i.e. overall survival) or to the date of censoring (date last known to be alive) for censored patients regardless of treatment arm.

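### Median PFS follow-up is taken from censored patients only, which tends to make Arm B look about 2 months less followed than Arm A; the pooled OS figure is also short, by an amount set by the death rate.

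*SAP*

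**What the plan says.** **PFS.** SAP 4.2.2.2, under Additional supportive summaries, defines duration of follow-up as the median time from randomization to censoring, "in censored (not progressed) patients only, presented by treatment group". The same paragraphs plan other completeness checks: prematurely censored patients by arm, missed consecutive assessments by group, and the statement that "summary statistics will be given for the number of days from censoring to DCO for all censored patients".

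**OS.** SAP 4.2.2.7 summarises follow-up by medians over every patient. Those who have died contribute their survival time, and the others are counted "to the date of censoring (date last known to be alive) for censored patients regardless of treatment arm". The closing words read as one figure over both arms.

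**Reverse Kaplan-Meier.** In SAP 4.2.2.2, under PFS sensitivity analyses, the missed-assessment analysis comes with a "Kaplan-Meier plot of the time to censoring where the censoring indicator of the primary PFS analysis is reversed". That is the reverse Kaplan-Meier curve. The sentence states neither a median nor a by-arm presentation, and it does not call the curve a follow-up summary. Nothing equivalent is planned for OS.

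**The concern.** Median follow-up is what a reader uses to judge how long patients were observed and whether the arms were observed equally. The second question matters here because the trial is open-label and Arm B treatment stops after at most 6 cycles, while Arm A treatment continues.

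Restricting the PFS figure to censored patients conditions on the outcome. A patient who entered early has longer potential follow-up and so more time to progress or die and leave the censored group. Those who remain are weighted towards shorter potential follow-up, and the weighting is stronger where the event rate is higher. The design assumes that Arm B's event rate is three times Arm A's, so the shortfall differs by arm even if observation is identical.

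For OS the mechanism is different. Treating a death as the end of follow-up shortens the median whenever patients die.

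**Working it through.** **Design figure first.** The documents give no median follow-up, so the nearest stated figure is power: "The study is sized to achieve more than 95% power to detect a hazard ratio of 0.333 in PFS". With 50 events, 1:1 allocation and two-sided 0.05, power = Φ(|ln 0.333|·√(50/4) − 1.96) = Φ(3.888 − 1.960) = Φ(1.928) = 97.3%. With the planned interim at 38/50 it is 97.1%. The stated figure reproduces.

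**Inputs.**
- SAP 1.3: 75 per arm, exponential PFS with medians 90 (A) and 30 (B) months, accrual 30 months, dropout 5% by 14 months, final analysis at about 53 months.
- Protocol 9.2: dropout about 5% by the final PFS analysis, modelled here as 5% by 38 months.
- Protocol 4.4: final analysis actually at about 45 months.
- Assumptions: uniform accrual and exponential dropout.

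Both 45 and 53 months are shown because, with SAP dropout, the expected events are 75 × (0.193 + 0.466) = 49.4 at 45 months and 75 × (0.236 + 0.543) = 58.4 at 53 months.

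**PFS without dropout (closed form).** With the cut-off at month T, potential follow-up is uniform on (T − 30, T), with median T − 15. A patient with potential follow-up u is still censored with probability e^(−λu). The censored-only median m therefore solves e^(−λm) = ½[e^(−λ(T−30)) + e^(−λT)].
- Arm B, λ = ln 2/30 = 0.02310, T = 45: ½(0.7071 + 0.3536) = 0.5303, so m = 27.45 against 30. Shortfall 2.55.
- Arm A, λ = ln 2/90 = 0.00770, T = 45: ½(0.8909 + 0.7071) = 0.7990, so m = 29.14 against 30. Shortfall 0.86.
- False gap between arms: 2.55 − 0.86 = 1.69 months. At T = 53 the shortfalls are the same, because changing T rescales both exponentials equally.

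**PFS with dropout.** Let δ be the dropout rate, for example −ln(0.95)/14 = 0.00366 per month. The censoring time has survivor function G(c) = e^(−δc)·min{1, (T − c)/30}. Reverse Kaplan-Meier estimates G, so its median solves G = 0.5 in both arms. The censored-only median is that of the censoring density weighted by e^(−λc). Solved numerically, in months:

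| Cut-off | Dropout | Reverse KM, both arms | Censored-only A (short by) | Censored-only B (short by) | False A − B gap |
|---|---|---|---|---|---|
| 45 | 5% by 14 mo | 28.4 | 27.4 (1.0) | 25.4 (2.9) | 1.9 |
| 45 | 5% by 38 mo | 29.4 | 28.5 (0.9) | 26.7 (2.7) | 1.8 |
| 53 | 5% by 14 mo | 35.9 | 34.8 (1.1) | 32.5 (3.3) | 2.2 |
| 53 | 5% by 38 mo | 37.2 | 36.3 (1.0) | 34.4 (2.9) | 1.9 |

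Shortfalls and gaps are taken before rounding. Simulation of 400,000 patients per arm agrees to within 0.1 month.

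**One trial of 75 per arm** (4,000 simulated trials, SAP dropout). The mean A − B gap is 1.8 months (SD 3.1) at 45 months and 2.1 (SD 3.3) at 53 months for censored-only. For reverse Kaplan-Meier it is −0.1 and −0.2. On a normal approximation, Φ(−2.07/3.28) = 26% of trials at 53 months would show no Arm B shortfall.

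**Visit-based censoring.** SAP Table 4 censors PFS at the last adequate assessment, and visits run every 12 and then 24 weeks. The medians then fall on visit dates. At 45 and 53 months the censored-only gap is 0 or 5.5 months depending on scenario, while reverse Kaplan-Meier is equal between arms in each. Reverse Kaplan-Meier then measures assessment follow-up: 33.1 months at T = 53, against true follow-up of 35.9.

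**OS, pooled, SAP dropout.** The documents give no OS rate, so a range is assumed:

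| Assumed 3-year OS | All-patient median, T = 53 (reverse KM 35.9) | Short by | All-patient median, T = 45 (reverse KM about 28.4) | Short by |
|---|---|---|---|---|
| 95% | 35.1 | 0.8 | 27.7 | 0.7 |
| 90% | 34.2 | 1.7 | 27.0 | 1.3 |
| 80% | 32.3 | 3.6 | 25.7 | 2.6 |
| 70% | 30.4 | 5.5 | 24.2 | 4.2 |

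**The case against.** The strongest reply is that little hangs on this. Maturity in this plan is defined by events (25.3% maturity, 76% information fraction), not by median follow-up. The SAP says openly which patients enter each figure, and it plans separate completeness summaries. That all stands, and it is why the point concerns a descriptive table only.

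A second reply is that the remedy is mostly there already. The reversed-indicator curve is planned for PFS. SAP 4.2.2.1 says that Kaplan-Meier plots of time-to-event endpoints will show medians and 95% CIs by arm. If that convention covers the reversed plot, which is arguable, the by-arm PFS median is already an output. What is missing is its use as the follow-up figure, and any counterpart for OS.

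Third, at 75 per arm the artefact is smaller than chance variation, so the table need not show Arm B as shorter. This also stands. The effect is a systematic tendency, not a certain result.

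A reader might infer that the OS summary too makes the arms look unequal. The text does not support that: the figure reads as pooled, and a pooled figure cannot differ by arm. A reader might also infer that reverse Kaplan-Meier recovers true PFS follow-up. It does not: PFS is censored at the last adequate assessment, before new therapy or before missed visits, and the estimator assumes non-informative censoring.

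**Conclusion.** The point holds as a minor reporting improvement. The censored-only PFS median understates follow-up by about 1 month in Arm A and about 2.5 to 3.3 months in Arm B. That is a false between-arm difference of about 2 months (1.7 to 2.2) when true follow-up is equal. These sizes rest on the design medians, uniform accrual, the stated dropout assumptions and continuous assessment. With visit-based censoring the size varies, and in a single trial of this size the difference is within chance (SD about 3 months).

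The pooled OS figure understates follow-up by an amount that depends on the death rate: 0.7 to 5.5 months over assumed 3-year OS of 95% to 70%. It says nothing about balance between arms.

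It would be wrong to read this as a threat to the primary result. No test, hazard ratio, alpha level or event count uses these summaries.

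**What to change.** For PFS, report by arm the median and 95% CI from the reversed-indicator Kaplan-Meier curve already planned, and label it as the follow-up summary. Note beside it that it measures follow-up to the last adequate assessment and assumes non-informative censoring. For OS, add the same reverse Kaplan-Meier summary by arm, with deaths treated as censored. The existing summaries can stay if each is labelled with the patients it includes.

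The cost is two table rows from data already derived. The timing needs stating. SAP version 2.0 is dated 19 December 2023, and the protocol synopsis records that the 03 January 2024 data cut-off became the final analysis and that the study was unblinded. The addition should therefore be presented as a labelled reporting item, not as pre-specified.
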